# Abbreviations

AE	Adverse Event
ALP	Alkaline Phosphatase
ALT	Alanine Aminotransferase
AML	Acute myeloid leukemia
APTT	Activated Partial Thromboplastin Time
Ara-C	Cytosine arabinoside
AST	Aspartate Aminotransferase
BM	Bone marrow
BP	Blood Pressure
bpm	Beats per minute
BUN	Blood Urea Nitrogen
°C	Celsius
cm	centimeter
CRF	Case Report Form
CTCAE	Common Terminology Criteria for Adverse Events
DLT	Dose limiting toxicity
ECG	Electrocardiogram
EFS	Event Free Survival
ECOG	Eastern Cooperative Oncology Group
HR	Heart rate
INR	International Normalized Ratio
IWG	International Working Group
kg	Kilogram
Max	Maximum
MCH	Mean Corpuscular Hemoglobin
MCHC	Mean Corpuscular Hemoglobin Concentration
MDS	Myelodysplastic Syndrome
MedDRA	Medical Dictionary for Regulatory Activities
mmHg	millimeter of mercury
Min	Minimum
MTD	Maximum tolerated dose
NCI	National Cancer Institute
ORR	Objective response rate
OS	Overall survival
PBMC	Peripheral blood mononuclear cells
PK	Pharmacokinetic
PT	Prothrombin Time
RBC	Red Blood Cells
RFS	Relapse Free Survival
RP2D	Recommended Phase II Dose
SAE	Serious Adverse Event
SAP	Statistical Analysis Plan
SD	Standard Deviation
SMC	Safety Monitoring Committee
TEAE	Treatment-Emergent Adverse Event

WHO	World Health Organization
WBC	White Blood Cells

# 1 Introduction

This document presents the statistical analysis plan (SAP) for BerGenBio AS, Protocol No. BGBC003 study submitted in four countries:

- Germany: A Phase Ib/II multicenter open-label study of BGB324(bemcentinib) as a single agent and in combination with cytarabine or decitabine in patients with Acute Myeloid Leukemia (AML) or as a single agent in patients with myelodysplastic syndrome. Final protocol dated 04AUG2020 (Version 10.0).
- Norway: A Phase Ib/II multicenter open-label study of bemcentinib (BGB324) as a single agent and in combination with cytarabine or decitabine in patients with acute myeloid leukemia (AML) or as a single agent in patients with myelodysplastic syndrome (MDS). Final protocol dated 04AUG2020 (Version 8.0).
- United States: An open label, multicentre, phase I/Ib/II study of BGB324 (bemcentinib) administered as a single agent or in combination with cytarabine or decitabine in patients with acute myeloid leukemia (AML) or as a single agent in patients with myelodysplastic syndrome (MDS). Final protocol dated 04SEP2020 (Version 9.0)
- Italy: An open label, multicentre, phase Ib/II study of BGB324(bemcentinib) administered as a single agent or in combination with cytarabine or decitabine in patients with acute myeloid leukemia or as a single agent in patients with myelodysplastic syndrome. Final protocol dated 23MAR2020 (Version 4.0)

The SAP provides the description of the final analyses for all 4 protocols listed above. The data will be analysed together as a unique single study taken into account the individuality of each protocol.

# 2 Study Objectives

## 2.1 Primary objectives

The primary objectives of this study are:

### Part A:

- In Norway: To identify the maximum tolerated dose (MTD) and/or Recommande Phase 2 dose (RP2D) of BGB324 (bemcentinib) in patients with relapsed or refractory AML or high risk MDS patients.
- In US and Italy: To identify the maximum tolerated dose (MTD) of bemcentinib in AML patients who have received previous treatment with cytotoxic chemotherapy (with or without hematopoietic stem cell transplantation) or a targeted or biologic agent (e.g. hypomethylating agent, tyrosine kinase inhibitor, antibody), and have relapsed after or have been refractory to treatment with such prior therapy.
- In Germany: To identify the maximum tolerated dose (MTD) of bemcentinib in AML patients who have received previous treatment with cytotoxic chemotherapy (with or without hematopoietic stem cell transplantation) or a gene expression modulator, such as a demethylating agent, and have relapsed after or have been refractory to treatment with that therapy.

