7.2.3. Selection of the Starting Dose for Clinical Study BGBC003

Bemcentinib clinical development studies to date have involved two formulations. The first study in healthy volunteers, Study BGBC001, used Formulation 1. Study BGBC004, in patients with non-small cell lung cancer has used Formulation 2 and given bemcentinib when patients have fasted. This study, BGBC003, will evaluate both Formulation 1 (taken when patients are fed), and Formulation 2 (taken when patients are fasted). Please see Section 7.2.3.1 and the current version of the bemcentinib IB for more details.

In Study BGBC001, 32 subjects received doses of bemcentinib in the range 50 to 1500 mg under fasted conditions, of which seven also received the same dose of bemcentinib under fed conditions. The time to maximum concentration (t_{max}) and the apparent $t_{1/2}$ were generally comparable between fed and fasted conditions; t_{max} ranged from 6 to 30 hours and $t_{1/2}$ ranged from 30.2 to 77.2 hours (except in one subject where $t_{1/2}$ was reliably estimated as 165 hours). There was an increase in systemic exposure to bemcentinib in three subjects, no appreciable change in three subjects and an apparent reduction in systemic exposure in one subject when bemcentinib was given with food compared to under fasted conditions.

Overall, C_{max} and area under the curve from time zero to 48 hours (AUC_{0-48h}) under fed conditions were 29% and 21% greater, respectively compared to fasted conditions; however, the 95% confidence interval (CI) of the ratio (fed/fasted) included 100%, indicating that the apparent effect of food was not statistically significant. The elimination of bemcentinib was slow with a $t_{1/2}$ of longer than 24 hours. A consequence of this prolonged $t_{1/2}$ is the delay in the time taken to achieve steady state, which is estimated to be approximately two weeks following the initiation of bemcentinib administration. Such a delay would not be therapeutically acceptable in patients with advanced cancers.

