8.1. Objectives

8.1.1. Primary Objectives

Part A

To identify the maximum tolerated dose (MTD) of bemcentinib in AML patients who have received previous treatment with cytotoxic chemotherapy (with or without hematopoietic stem cell transplantation) or a targeted or biologic agent (e.g. hypomethylating agent, tyrosine kinase inhibitor, antibody), and have relapsed after or have been refractory to treatment with such prior therapy.

Part B

To identify the safety and tolerability of bemcentinib as a single agent in patients with AML or MDS (Parts B1 and B4), or in combination with low dose cytarabine (Part B2 and Part B5) or decitabine (Part B3), in patients with AML who are unsuitable for intensive chemotherapy as a result of advanced age or existing co-morbidities.

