### Phase I DLT Assessment Period

During the dose-escalation phase (Part A), safety, tolerability, PK, and preliminary clinical activity of BGB324 will be assessed, and the MTD established, in patients with AML who have received previous treatment with cytotoxic chemotherapy or a targeted or biologic agent (e.g. hypomethylating agent, tyrosine kinase inhibitor, antibody) or a gene expression modulator, such as a demethylating agent and have relapsed after or have been refractory to treatment with such prior therapy or in high risk MDS. Patients suitable for intensive chemotherapy should be in second or subsequent relapse or be refractory to at least two induction regimens. Patients receiving an allograft in first remission would be eligible at the time of relapse.

A loading dose (Cohort 1) of 200 mg administered on Cycle 1, Days 1, 2 and 3 followed by a daily maintenance dose of 100 mg during continuous 21-day treatment cycles will be evaluated. This dose may be escalated as agreed by the SMC to a maximum daily loading dose of 400 mg on Days 1, 2 and 3 followed by a maximum daily maintenance dose of 200 mg. At least three evaluable patients will be entered per cohort.(see Section 9 of the individuals protocols). At least three evaluable patients will be entered per cohort.

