## 5 Statistical Methodology

### 5.1 Planned Analyses

Disposition analyses will be carried out using the Enrolled Population. Demographic and baseline characteristics analyses will be carried out using the Safety Analysis Set. Safety analyses will be carried out using the Safety Analysis Set. Efficacy analyses will be carried out using the Efficacy Analysis Population.

Summary statistics will be presented for continuous variables, by way of n, mean, standard deviation (SD), median, minimum (Min) and maximum (Max) and by way of group frequencies and percentages for categories of categorical variables. No statistical comparison of dose levels or treatment groups will be performed. Percentages will be calculated using the total patients per dose cohort in the given population unless otherwise noted.

All data from this study will be presented in data listings. All listings will be sorted by dose level or treatment group and patient.

Baseline will be defined as the last assessment prior to study drug administration. Typically this will be Cycle 1 Day 1. Where calculated, absolute change from baseline will be presented using the following formula for each parameter: Value at the visit/timepoint – value at baseline.

Data will be presented by dose/cohort and overall in Part A and by treatment group (AML (B1: BGB324 400/200 mg Single agent; B2: BGB324 400/200 mg + Cytarabine; B3: BGB324 400/200 mg + Decitabine; B5: BGB324 400/200 mg + Cytarabine) and MDS (B4: BGB324 400/200 mg) ) and overall in Part B.

Where appropriate, the data for patients who received the MTD during Part A will be combined with that for patients who received the MTD in Part B for the purpose of data summarisation. A clear distinction will be made in the relevant Tables to differentiate between the cohort who received the MTD during the dose escalation phase of Part A, the MTD cohort from the cohort expansion phase in Part A, and the combined MTD cohort.

Any patient treated with bemcentinib beyond disease progression will be followed for the same safety and efficacy assessments as for all other patients enrolled into the study. The data for patients treated beyond progression will be presented in both a combined output (with all patients) and a separate output (reflecting a new period of analysis with the data collected in this period). All data collected will be included in the study CSR and may be presented at congress/symposia.

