## 5.7 Efficacy Analysis

The endpoints to be analysed in the efficacy analysis are:

**Objective response rate [ORR]** : Proportion of patients with a best objective response such as, CR (Complete Remission), Cri (Complete Remission with Incomplete hematologic Recovery), CRp (Complete Remission with Incomplete Platelet Recovery), CRh and PR(Partial Remission) for AML patients and CR, PR, MR(Marrow Response), PMR(Partial Marrow Response) for MDS patients;

CRh is defined as, CR (<5% myeloblasts and 0% blasts in the peripheral blood) with partial hematologic recovery, defined as meeting CR criteria but with ANC > 0.5 10^9/L and platelets > 50 10^9/L responses for patients with AML.

Best Objective Response (BOR) = Best response obtain during the study participation for a patient;

**Disease control Rate (Objective Response + SD) [DCR]**: Proportion of patients with a best objective response such as, CR, CRi, CRp, CRh and PR for AML patients and CR, PR, MR, PMR for MDS patients, + SD (stable disease) as an estimate of clinical benefit;

The ORR will be summarized by;

- Age group (<75 years, >= 75);
- AML Disease Cytogenetic Profile (Favourable, Intermediate, Adverse and not done);

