### 6.3.2 Section 14.2: Efficacy Analysis

Table 14.2.1.1	Objective Response Rate – Part A (Efficacy Population)
Table 14.2.1.2	Objective Response Rate – Part B (Efficacy Population)
Table 14.2.2.1	Relapse Free Survival – Summary – Part B (Efficacy Population)
Table 14.2.3.1	Event Free Survival – Summary – Part B (Efficacy Population)
Table 14.2.4.1	Overall Survival – Kaplan Meier Analysis – Part B (Efficacy Population)

Table 14.2.5.1.1	Objective Response Rate by Age Group – Part A (Efficacy Population)
Table 14.2.5.1.2	Objective Response Rate by Age Group – Part B (Efficacy Population)
Table 14.2.5.1.3	Objective Response Rate by AML Disease Cytogenetic profile – Part A (Efficacy Population)
Table 14.2.5.1.4	Objective Response Rate by AML Disease Cytogenetic profile – Part B (Efficacy Population)

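### SAP Part A admits high-risk MDS under the Norwegian protocol but plans a response rate with no AML/MDS split, although the two diseases are scored on different response lists

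*SAP*

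**What the plan says.** **Who may enter Part A.** SAP 2.1 gives the Norwegian objective as "in patients with relapsed or refractory AML or high risk MDS patients". The Part A design text in SAP 4.1 repeats this: after describing treated AML it covers patients who "have been refractory to treatment with such prior therapy or in high risk MDS". SAP 2.1 gives AML-only objectives for the US, Italy and Germany, and the US protocol agrees (Protocol 8.1.1): "To identify the maximum tolerated dose (MTD) of bemcentinib in AML patients who have received previous treatment".

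**How the data are combined.** SAP 1 treats the four country protocols as one study, with a general remark that the particular features of each will be respected. No Part A rule follows from that remark.

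**How Part A is displayed.** SAP 5.1: "Data will be presented by dose/cohort and overall in Part A". The same sentence splits Part B by treatment group and sets MDS (B4) apart from the AML groups.

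**What counts as a response.** SAP 5.7 lists CR, CRi, CRp, CRh and PR for AML, but "CR, PR, MR(Marrow Response), PMR(Partial Marrow Response) for MDS patients".

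**Which tables use it.** SAP 6.3.2 lists Part A objective response in total (14.2.1.1), by age group (14.2.5.1.1) and by AML cytogenetic profile (14.2.5.1.3). None is by disease. The relapse-free, event-free and overall survival tables are for Part B only, so the response tables are the only Part A efficacy tables.

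**The concern.** A response rate can be read only if every patient in the denominator is judged by one definition. Here the denominator may hold two diseases, each with its own list of qualifying categories. The resulting rate would describe neither relapsed or refractory AML nor high-risk MDS. The SAP treats the distinction as necessary in Part B and is silent on it in Part A.

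The stake is interpretation. Dose cohorts in a 3+3 design hold three or six patients, so one responder of the other disease can change what a cohort appears to show. A reader comparing Part A with the AML cohort B1 could credit AML with a response that came from MDS.

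**Working it through.** **The plan's own Part A figure.** The only Part A operating figures are the 3+3 escalation probabilities in SAP 4.9. The formula is (1−p)³ + 3p(1−p)² × (1−p)³. At p = 0.20 this is 0.512 + 0.384 × 0.512 = 0.709. Across 20, 30, 40, 50 and 60% it gives 70.9, 49.4, 30.9, 17.2 and 8.2%, against the stated 71, 49, 31, 17 and 8%. These reproduce. They concern toxicity, so a disease split in the response tables changes none of them. The response-rate sizing in SAP 4.9 covers Part B only.

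**The response rules side by side** (Protocol Appendices 5 and 6, SAP 5.7).

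- AML partial remission needs marrow blasts to fall by at least half into the 5–25% range, and the blood counts must also meet every CR requirement.
- MDS marrow CR needs blasts at or below 5% with a fall of at least half. No count recovery is required; improvement in counts is simply noted if present. I read the SAP's MR as this category, which is an assumption because the SAP does not define MR.
- PMR also counts as an MDS response. It has no entry in Appendix 6 and no definition in the SAP.

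An AML patient whose blasts halve into the 5–25% range without count recovery is therefore not a PR. An MDS patient can count on a marrow criterion alone.

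**Which tables are exposed.** Tables 14.2.1.1 and 14.2.5.1.1 carry no disease restriction, so followed as written they would add responders from both lists. Table 14.2.5.1.3 is AML by title, but the SAP does not say whether MDS patients are left out of it. The disease control rate in SAP 5.7 is built on the same two lists and inherits the problem.

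**Illustration 1, one cohort (invented counts).** Take five AML patients without response and one MDS patient with a marrow response.

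- Combined: 1/6 = 16.7%, exact 95% interval 0.4% to 64.1%.
- AML alone: 0/5 = 0%, exact 95% interval 0% to 52.2%.

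**Illustration 2, Part A as a whole.** Let f be the MDS share. Combined rate = (1−f) × AML rate + f × MDS rate. I take 5% for AML (the null rate in Protocol 16.5.2) and 20% to 40% for MDS. The MDS rates and f are assumptions; the documents give neither.

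| f | MDS 20% | MDS 40% |
|---|---|---|
| 0 | 5% | 5% |
| 0.10 | 0.045 + 0.020 = 6.5% | 0.045 + 0.040 = 8.5% |
| 0.20 | 0.040 + 0.040 = 8.0% | 0.040 + 0.080 = 12.0% |
| 0.30 | 0.035 + 0.060 = 9.5% | 0.035 + 0.120 = 15.5% |

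The distortion is nil at f = 0, and nil if the two diseases respond at the same rate.

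**The case against.** The case against has real weight.

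- **Eligible is not enrolled.** The documents show that one country's Part A permitted high-risk MDS. They do not show that any such patient entered, and the Norwegian protocol was not supplied. This stands and makes the point conditional.
- **Nothing is decided on Part A response.** Its primary objective is the MTD, efficacy is to be explored, and the planned response test concerns Part B. This also stands and limits the consequence to interpretation.
- **A reader could recover the split.** Cancer type is summarised (SAP 5.4), and cancer history and individual responses are listed (SAP 6.4). The table shells are a separate file and might already separate the diseases. This softens the point, but a headline rate should not need reconstruction from listings, and the SAP text states no split.
- **Part A patients join B1 only if they meet B1 eligibility** (SAP 4.5.2, Protocol 16.4.1), and B1 requires AML (Protocol 10.1). This stands: MDS patients are already kept out of the B1 analysis. The combined-MTD summary in SAP 5.1 is hedged as applying where appropriate, but names no disease condition.

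Three stronger readings are tempting and are not supported.

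- A reader might infer that a cleared marrow with low counts is a response in MDS but never in AML. Appendix 5 defines CRi as marrow clearance with low counts, and CRi is on the AML list.
- A reader might infer that the MDS rules are looser throughout. Appendix 6 asks more for MDS CR, including haemoglobin of at least 11 g/dL, neutrophils of at least 1.5 × 10⁹/L (AML: 1.0) and confirmation at successive assessments. The lists differ, but not always in one direction.
- A reader might infer that the overall column must be replaced by subtotals for the two bemcentinib formulations. Formulation 2 entered in an additional escalation cohort, and the stated starting regimens differ (400 mg on two days then 100 mg daily, against 200 mg on three days then 100 mg daily). Display by dose/cohort can therefore separate them. The documents show no single regimen given in both. An overall column in any dose escalation spans different exposures, so replacing it is a preference.

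**Conclusion.** The point holds in a conditional and limited form. As written, the SAP lets two diseases into Part A, scores response on two different lists, and plans no split. If one or more MDS patients enrolled, the Part A objective response and disease control rates would mix the two. On the assumed rates above, a 10% to 30% MDS share would move a 5% AML rate to between 6.5% and 15.5%. In a six-patient cohort a single MDS responder can supply the whole observed rate. If no MDS patient enrolled, there is no effect.

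The conclusion rests on the SAP text without the table shells, and on reading MR as the marrow CR of Appendix 6. The MTD, alpha, power and sample size are unaffected. The change is still worth making, because it is cheap and removes a rate that would describe neither disease.

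**What to change.** 1. In SAP 5.1 and Tables 14.2.1.1 and 14.2.5.1.1, present Part A objective response and disease control separately for AML and MDS within each dose cohort and overall, with no combined AML and MDS response rate. Alternatively, state in SAP 5.1 that no MDS patient was enrolled in Part A. Protocol 16.8 records Part A as complete, so the sponsor can check this directly.
2. In the combined-MTD paragraph of SAP 5.1, add that efficacy data from Part A and Part B are combined only for patients with the same disease. This brings it into line with the B1 eligibility condition in SAP 4.5.2.

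The cost is two sentences in the SAP and a few table columns, since cancer type is already to be summarised. The drawback is small cells: some will hold one patient or none, and should be shown as counts with exact intervals.

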**Part B:**

- To identify the safety and tolerability of bemcentinib, as a single agent in patients with AML (Part B1) or MDS (Part B2) and in combination with low dose cytarabine (Part B2 and Part B5) or decitabine (Part B3),
  - In Norway, US and Germany: in patients with AML who are unsuitable for intensive chemotherapy as a result of advanced age or existing co-morbidities.
  - In Italy: in patients with AML who are unsuitable for intensive chemotherapy.

## 2.2 Secondary objectives

The secondary objectives of this study are:

**Part A:**

- To identify the dose limiting toxicity (DLT) profile of bemcentinib
- To explore the safety, tolerability and efficacy of bemcentinib
- To characterise the pharmacokinetic (PK) profile of bemcentinib

**Part B:**

- To explore the efficacy of bemcentinib as a single agent in patients with AML or MDS (part B1 and B4)
- To explore the efficacy of bemcentinib in combination with low dose cytarabine (Part B2 and Part B5) or decitabine (Part B3) in patients with AML who are unsuitable for intensive chemotherapy as a result of advanced age or existing co-morbidities or not.
- To evaluate bemcentinib PK (all Part B cohorts)

## 2.3 Exploratory objectives

The exploratory objectives of this study are:

- To identify and evaluate potential predictive biomarkers, e.g. soluble AXL (sAXL) and other associated soluble biomarkers. Pre-treatment levels of biomarkers will be correlated with clinical endpoints
- To establish the effects of bemcentinib on relevant biological endpoints in peripheral blood (including sAXL peripheral blood mononuclear cells [PBMC]) and BM samples
- To assess pharmacodynamic biomarkers in tissue and blood to support the clinical development of bemcentinib
- To evaluate other biomarkers relevant to the investigational agents for exploratory purposes

# 3 Endpoints

## 3.1 Safety endpoints

Safety and tolerability will be assessed by conducting the following safety assessments at pre-defined time-points during the study:

- Treatment emergent adverse events (TEAE)
- Physical examination

- Vital signs including blood pressure (BP), heart rate (HR), respiration rate and temperature
- Electrocardiogram (ECG)
- Echocardiogram
- Laboratory findings including clinical chemistry, hematology and urinalysis

### 3.2 Efficacy endpoints

In AML, efficacy endpoints will be measured using objective response criteria, in evaluable patients.

- Objective Response (OR) or Stable Disease (SD) according to the revised recommendations of the International Working Group (IWG) in AML [Cheson, BGBC003 v8.0 (NO); 04 August 2020 CONFIDENTIAL Page 37 of 113 2003 and Döhner, 2017] (see Appendix 5 of the protocol). SD is defined as having unchanged disease for at least 3 treatment cycles.
- Proportion of patients with an OR + SD as an estimate of clinical benefit.
- Relapse Free Survival
- Event Free Survival
- Overall Survival
- To explore the correlation between baseline biomarker levels and clinical endpoints

In MDS, efficacy endpoints will be measured using the following response criteria.

- OR or SD according to the revised recommendations of the IWG in MDS (see Appendix 6 of the protocol). SD is defined as failure to achieve at least PR but not evidence of PD for at least 3 treatment cycles.
- Proportion of patients with an OR + SD as an estimate of clinical benefit.
- Relapse Free Survival
- Event Free Survival
- Overall Survival
- To explore the correlation between baseline biomarker levels and clinical endpoints

